Serum concentration for ART drugs ^[38]	X ^[32]	X	
Anti-idiotypic antibodies to PRO 140	X ^[32]	X	X
HIV Genotyping Assay			X
Trofile® DNA/RNA and PhenoSense® Entry Assay		X	X
Blood sample collection for Exploratory/Confirmatory analysis ^[38]		X	X
PRO 140 Administration	X ^[39]	X ^[40]	
Subject drug dispensing/accountability ^[41]	X	X	
Antiretroviral Regimen ^[42]		X	X
Injection Site Reaction Assessment ^[43]	X ^[32]	X	
Injection Site Pain Assessment (VAS) ^[44]	X ^[32]	X	
Adverse Events ^[33]	X	X	X
Concomitant Medications	X	X	X

- [32] In-clinic assessment(s) should be performed at least once every 4 weeks from TE108 onwards.
- [33] Subjects should be instructed to report any new AEs that occur between clinic visits to site promptly
- [34] Performed by Principal Investigator (or designee) when subject comes to clinic. NOTE: The neurological assessment tool is based on the three question survey used by Simioni et al. (Simioni S, 2010). Additional neurological assessment modalities may be used as per Investigator's discretion.
- [35] Blood pressure, heart rate, respiration rate, temperature assessed before and 15 minutes after study treatment administered at clinic
- [36] Hemoglobin, Hematocrit (HCT), Red Blood Cells (RBC), White Blood Cells (WBC) with total and differential count, Absolute Neutrophil Count (ANC) and platelets.
- [37] Serum Biochemistry:
Hepatic function indicators: total and direct bilirubin, alkaline phosphatase, aspartate aminotransferase (AST), alanine aminotransferase (ALT), total protein, lactate dehydrogenase (LDH)Renal function indicators: BUN, creatinine. Electrolytes: sodium, potassium, chloride, calcium and bicarbonate. Other: glucose (random), cholesterol (total)
- [38] Sample may be collected on ad hoc basis, as per discretion of Sponsor/Investigator during the Treatment Phase
- [39] Subjects will attend clinic visits, and receive PRO 140 treatment in clinic, on weeks when lab samples are required (at least once every 4 weeks). Subjects trained to perform self-administration of study treatment may do so outside of the clinic (at home) on weeks when no lab samples are required.
- [40] Study treatment should be administered at clinic.
- [41] PRO 140 for subsequent self-administration visits will be provided to subjects during treatment visits at clinic; used vials from prior self-administration must be collected and accounted for (see [Section 4.2.2](#)).
- [42] All study subjects will re-initiate their previous antiretroviral regimen: (1) One week prior to the end of Treatment Extension Phase, or (2) Anytime during the Treatment Extension Phase, if virologic failure occurs or have met any other criteria for discontinuation of study treatment as specified in the protocol.
- [43] As assessed by Investigator when study treatment administered at the clinic.
- [44] Subject-perceived injection site pain (average pain since last treatment) will be assessed using the Pain Visual Analog Scale (VAS) prior to each study treatment administration for subjects randomized to PRO 140.
- [45] Should be performed at least once every 12 weeks from TE160 onwards.

Table 4-9: Schedule of Assessments –Follow-Up (FU) Phase

(a) Subjects who do NOT experience virologic failure

Procedure/Assessments	Follow-Up Visit -1	Follow-Up Visit -2
	NVF-EFU1	NVF-EFU2
Window Period	2 weeks (±3 days) after TE161	4 weeks (±3 days) after TE161
Physical Examination	X ^[1]	X ^[1]
Vital Signs	X	X
Plasma HIV-1 RNA level	X	X
TruCount T assay	X	X
Previously used Antiretroviral Regimen	X	X
Adverse Events	X	X
Concomitant Medications	X	X
Anti-idiotypic Antibodies to PRO 140		X

[1] Symptom-directed physical examination

(b) Subjects who experience virologic failure

- Short term follow up visits

Procedure/Assessments	Follow-Up Visit -1	Follow-Up Visit -2	Follow-Up Visit -3 ^[1]
	VF-EFU1	VF-EFU2	VF-EFU3
Window Period	4 weeks (±7 days) after VF	8 weeks (±7 days) after VF	12 weeks (±7 days) after VF
Physical Examination	X ^[2]	X ^[2]	X ^[2]
Vital Signs	X	X	X
Plasma HIV-1 RNA level	X	X	X
TruCount T assay	X	X	X
Previously used Antiretroviral Regimen	X	X	X
Adverse Events	X	X	X
Concomitant Medications	X	X	X
Anti-idiotypic Antibodies to PRO 140	X		

[1] Subject will be followed up every 4 weeks until viral suppression is achieved (i.e., plasma HIV-1 RNA levels to return back to <50 copies/mL). Subject will undergo additional follow-up visits every 4 weeks beyond VF-EFU3 visit, if viral suppression is not achieved at the end of VF-EFU3 visit.

[2] Symptom-directed physical examination

(c) Subjects who experience virologic failure

- Long term follow up visits

Procedure/Assessments	Long-Term Follow-Up Visit -1	Long-Term Follow-Up Visit -2
	VF-12mFU	VF-24mFU
Window Period	12 months (± 1 month) after VF visit	24 months (± 1 month) after VF visit
Assessment of cART changes ^[1]	X	X
Plasma HIV-1 RNA level	X	X
TruCount T assay	X	X
Trofile® DNA or RNA Assay ^[3]	X*	X*
PhenoSense® Entry Assay ^[4]	X*	X*
HIV-1 Drug Resistance Assay ^[5]	X*	X*

- [1] Any changes to the combination antiretroviral regimen since the viral re-suppression is achieved.
- [2] Monogram Biosciences Trofile® DNA or RNA (or both) assay will be performed depending on last known HIV-1 RNA levels.
- [3] Monogram Biosciences HIV-1 PhenoSense® Entry assay with AMD3100 (X4 inhibitor drug), Maraviroc and PRO 140 (R5 inhibitor drugs).
- [4] Monogram Biosciences GenoSure Archive® Assay or PhenoSense® GT (and PhenoSense® Integrase and GeneSeq Integrase testing, if applicable), will be performed depending on last known HIV-RNA levels.

*As per discretion if the investigator

4.1 SCREENING PHASE

4.1.1 Screening Visits 1 & 2

The subject will sign and date the informed consent form (ICF) and Health Insurance Portability Accountability Act (HIPAA) authorization (according to site policy and practices) prior to any study-related procedures.

The unique identification number (screening number) that was assigned for PRO 140_CD 01 study will continue to be used for this extension study.

Once the ICF has been signed, screening procedures and information will be obtained to confirm subject eligibility. Assessments that are in addition to those performed at T12 or T13 of the PRO 140_CD 01 protocol are noted below:

- Detailed medical history – SV1 (see [section 7.4](#)),
- Demographic information (see [section 7.3](#)),
- Collection of Blood Specimens (see [section 7.10](#)) for
 - Serum pregnancy test, for female subjects of childbearing potential. Childbearing potential is defined as someone who is not surgically sterile or is not more than one year past complete cessation of menstrual cycles (SV1)
 - Blood sample collection for Exploratory/Confirmatory analysis (SV2)
- Urine pregnancy test at second Screening Visit, for female subjects of childbearing potential (see [section 7.10.5](#))

All screening information will be fully documented in the subject's medical records (i.e., source documents).

- For consented subjects who do not meet eligibility criteria, a Screen Failure electronic Case Report Form (eCRF) will be completed. The Screen Failure eCRF will contain the following details: the subject identification number, the date of ICF signature, demographic information (see [section 7.3](#)), and the reason for screen failure. No additional information will be required for subjects who fail screening.
- For consented subjects who meet eligibility criteria, all required screening information will be transcribed onto the appropriate page of the eCRF.

Eligible subjects that are not enrolled within 14 days of Screening Visit 1 must enter the Follow-up Phase of PRO 140_CD 01 Treatment Substitution protocol.

4.2 TREATMENT EXTENSION PHASE

Treatment Extension Phase begins with an evaluation of results of laboratory samples collected during the Screening Phase. Subjects who meet all eligibility criteria, as per data gathered from Screening Phase are to be treated. All subjects who fail to meet eligibility criteria will be considered screen failures, exit the study without further evaluation and enter the Follow-up Phase of the PRO 140_CD 01 Treatment Substitution protocol.

Eligible subjects will receive PRO 140 weekly SC treatments, given every week (\pm 3 days) or until virologic failure, whichever occurs first.

PRO 140 will be administered as a 350 mg subcutaneous injection weekly. The study treatment (PRO 140 SC injections) will be administered by a qualified medical professional (MD, DO, PA, LPN, LVN, NP, RN, or CMA if permitted by state law) or subjects trained to perform self-administration of study treatment (see [section 6.4](#)).

Note: Patients enrolled under a previous Protocol (V.1.0-9.0) have the option of increasing their dose to receive 700mg weekly for the remainder of the Treatment Extension Phase.

All study subjects will re-initiate their previous antiretroviral regimen:

- One week prior to the end of Treatment Extension Phase, or
- Anytime during the Treatment Extension Phase, if virologic failure occurs or have met any other criteria for discontinuation of study treatment as specified in [section 5.2.1](#) of the protocol.

Note:

- In case of increase in plasma HIV-1 RNA levels above 200 copies/mL, subjects will return to clinic for another blood draw in-between the Treatment Visits for repeat plasma HIV-1 RNA levels, as per the discretion of the Investigator.
- Subjects who experience virologic failure (defined as two consecutive HIV-1 RNA levels of \geq 400 copies/ml separated by at least 3 days) at any time during the Treatment Extension Phase will undergo the Virologic Failure (VF) Visit assessments and enter the Follow-up Phase of the study.
- Subjects who meet any criteria (other than virologic failure) for discontinuation of study treatment as specified in [section 5.2.1](#) of the protocol, will undergo TE161 Visit assessments and enter the Follow-up Phase of the study.
- Subjects who do not experience virologic failure will enter the Follow-up Phase of the study at the end of 161-week Treatment Extension Phase.

Visits during the Treatment Extension Phase will commence on TE1, i.e. the date of first treatment, with weekly visits (\pm 3 days) thereafter.

4.2.1 Treatment Visit-1 (TE1)

The following assessments will be performed at the first treatment visit.

Pre-Treatment

- Confirmation of eligibility criteria by reviewing test results and other criteria assessments performed at the Screening Visits (see [section 7.2](#))
- Change in concomitant medications (see [section 7.5](#))
- Vital signs (see [section 7.9](#)),
- Any changes in medical history since Screening Visit (see [section 7.4](#)),
- Symptom-directed physical examination (see [section 7.6](#)),
- Neurological assessment (see [section 7.7](#))
- Quality of life assessment (see [section 7.8](#))
- Subject-perceived Injection Site Pain Assessment (see [section 7.13](#))
 - **Note:** *Subject-perceived injection site pain will be assessed using the Pain Visual Analog Scale (VAS) prior to study treatment administration assessing average pain since last treatment.*

Administration of PRO 140

PRO 140 350 mg is administered as subcutaneous injection in the abdomen weekly. A total of 350 mg (175 mg/mL) is delivered as two 1 mL injections on opposite sides of the abdomen. Subjects who were enrolled under a previous Protocol version and are still receiving the 350 mg dose, have the option of increasing their dose to 700mg for the remainder of the Treatment Extension Phase. PRO 140 700 mg is delivered as two 2 mL injections on opposite sides of the abdomen.

Note: Alternatively, the 700 mg dose may be delivered as four 1mL doses (two SC injections on opposite sides of abdomen) for those that experience discomfort with the 2mL injections (i.e. subjects with low body fat percentages).

The study treatment (PRO 140 SC injections) will be administered by a qualified medical professional (MD, DO, PA, LPN, LVN, NP, RN, or CMA if permitted by state law) or subjects trained to perform self-administration of study treatment.

Post-Treatment

- Injection Site Reaction Assessment (see [section 7.12](#))
 - **Note:** *To assess injection site reactions, the investigator will use the DAIDS AE grading table (refer to [section 17.3](#)).*
 - **Note:** *Performed when treatment visit occurs at clinic*
- Assessment of Adverse Events (AE) (see [section 9](#))
- Vital Signs (see [section 7.9](#)) will be assessed within 15 minutes of study treatment administration.

4.2.2 Treatment Visit-2 (TE2) to Visit-59 (TE59) – Bi-weekly Visits

The following assessments will be performed at each visit, unless otherwise specified:

- Assess for any Adverse Events and changes in Concomitant medications (see [section 9](#) and [7.5](#)),
- Symptom-directed physical examination (see [section 7.6](#)),
- Neurological Assessment (see [section 7.7](#))
 - **Note:** *Performed by Principal Investigator (or designee) when subject comes to clinic; additional neurological assessment modalities may be used as per Investigator's discretion.*
- Quality of Life Assessment (see [section 7.8](#))
 - **Note:** *Performed by Principal Investigator (or designee) when subject comes to clinic*
- Vital Signs (see [section 7.9](#))
 - **Note:** *Vitals not obtained when subject self-administers study treatment outside clinic*
- Collection of Blood Specimens (see [section 7.10](#)) for
 - Plasma HIV-1 RNA level
 - TruCount T Assay
 - PK sample for PRO 140
 - Serum concentration of ART drugs
 - Anti-idiotypic antibodies to PRO 140
 - Blood sample for exploratory analysis

- **Note:** *Lab samples to be collected at the time of clinic visit*
- Study Treatment Administration (PRO 140)
- **Note:** *Subjects trained to perform self-administration of study treatment may self-administer when clinic visit not required (no lab sample collection needed), at odd numbered treatment visits beyond TE2*
- Injection Site Reaction Assessment (see [section 7.12](#))
- **Note:** *To assess injection site reactions, the investigator will use the DAIDS AE grading table (see [section 17.3](#)).*
- **Note:** *Assessment will be performed when subject administered study treatment at clinic visit*
- Subject-perceived Injection Site Pain Assessment (see [section 7.13](#))
- **Note:** *Subject-perceived injection site pain will be assessed using the Pain Visual Analog Scale (VAS) prior to study treatment administration assessing average pain at injection site since last treatment.*
- **Note:** *Performed at the time of clinic visit.*

4.2.3 Treatment Visit-60 (TE60) onwards – Monthly Visits

Patients are required to have a clinic visit at least once every four weeks from TE60 onwards. Subjects will re-initiate previous antiretroviral regimen at end of treatment extension phase (one week prior to last PRO 140 treatment), if viral load remain suppressed.

The following assessments will be performed at every clinic visit:

- Assess for any Adverse Events and changes in Concomitant medications (see [section 9](#) and [7.5](#)),
- Symptom-directed physical examination (see [section 7.6](#)),
- Neurological Assessment (see [section 7.7](#))
- Vital Signs (see [section 7.9](#))
- **Note:** *Vitals not obtained when subject self-administers study treatment outside clinic*
- Study Treatment Administration (PRO 140)
- **Note:** *Subjects trained to perform self-administration of study treatment may self-administer when clinic visit not required (no lab sample collection needed)*

- Injection Site Reaction Assessment (see [section 7.12](#))
 - **Note:** *To assess injection site reactions, the investigator will use the DAIDS AE grading table (see [section 17.3](#)).*
 - **Note:** *Assessment will be performed when subject administered study treatment at clinic visit*
- Subject-perceived Injection Site Pain Assessment (see [section 7.13](#))
 - **Note:** *Subject-perceived injection site pain will be assessed using the Pain Visual Analog Scale (VAS) prior to study treatment administration assessing average pain at injection site since last treatment.*
 - **Note:** *Performed at the time of clinic visit.*
- Collection of Blood Specimens (see [section 7.10](#)) for
 - Plasma HIV-1 RNA level
 - TruCount T Assay
 - Routine CBC
 - Biochemistry
 - PK sample for PRO 140
 - Serum concentration of ART drugs
 - Anti-idiotypic antibodies to PRO 140
 - Blood sample for exploratory analysis
- **Note:** *Trofile® RNA or Trofile® DNA and PhenoSense Entry Assay will be performed at the last treatment visit (EOT)*
 - CCR5 Receptor Occupancy
- **Note:** *Blood will be taken prior to PRO 140 injection (trough sample) and 24-48 hours (peak sample) after the PRO 140 injection to check for CCR5 occupancy, and correlative analysis will be performed with PRO 140 PK concentration and HIV-1 RNA levels. This assessment will be performed up to 5 times at different treatment visits.*

4.2.4 Virologic Failure (VF) Visit

The following assessments will be performed for subjects who experience virologic failure at any time during the Treatment Extension Phase:

- Assess for any Adverse Events and changes in Concomitant medications (see [section 9](#) and [7.5](#)),
- Complete Physical Examination (see [section 7.6](#)),
- Vital Signs (see [section 7.9](#)),
- Neurological Assessment (see [section 7.7](#)),
- Collection of Blood Specimens (see [section 7.10](#)) for
 - Plasma HIV-1 RNA level
 - TruCount T Assay
 - HIV Genotyping Assay
 - Trofile® RNA or Trofile® DNA and PhenoSense Entry Assay
 - Anti-idiotypic antibodies to PRO 140
 - Routine CBC
 - Biochemistry
 - PK sample for PRO 140
 - Blood sample collection for Exploratory/Confirmatory analysis
- Re-initiate previous Antiretroviral Regimen

4.3 FOLLOW-UP PHASE

The duration of follow-up depends on the status of viral load suppression.

- Subjects who experience virologic failure will be followed up every 4 weeks until the viral load suppression is achieved (i.e., plasma HIV-1 RNA levels to return to <50 copies/mL)
- Subjects who do not experience virologic failure at the end of Treatment Extension Period, will be followed up every 2 weeks for total of 4 weeks.
- *Note: Virologic failure subjects will have a long term safety follow up visit once a year within 2 years of completing the last VF-FU visit.*

4.3.1 Follow-Up Visits

The following assessments will be performed at each follow-up visit, unless otherwise specified:

- Assess for any Adverse Events and changes in Concomitant medications (see [section 9](#) and [7.5](#)),
- Symptom-directed physical examination (see [section 7.6](#)) *at NVF-EFU and short term VF-EFU visits*,
- Vital Signs (see [section 7.9](#)),
- Collection of Blood Specimens (see [section 7.10](#)) for
 - Plasma HIV-1 RNA level
 - TruCount T Assay
 - Anti-idiotypic antibodies to PRO 140 *(NVF-EFU2 and VF-EFU1 visits)*
 - Trofile® DNA or RNA Assay *(VF-12mFU and VF-24mFU visits)*
 - PhenoSense® Entry Assay *(VF-12mFU and VF-24mFU visits)*
 - HIV-1 Drug Resistance Assay *(VF-12mFU and VF-24mFU visits)*

5 SUBJECT COMPLETION AND WITHDRAWAL

5.1 SUBJECT COMPLETION

- A subject who completes the Treatment Extension Phase (without virologic failure) and 4-week Non-Virologic Failure Follow-Up Phase will be considered as having completed the study.
- A subject who experiences virologic failure during the Treatment Extension Phase, undergoes the VF Visit assessments and is followed up until viral suppression is achieved, will be considered as having completed the study.

5.2 SUBJECT WITHDRAWAL

A subject who enters the Treatment Extension Phase but does not complete the study, as defined in [Section 5.1](#), is considered to have prematurely withdrawn from the Study.

All subjects have the right to withdraw at any point during treatment without prejudice to future care. It will be documented whether or not each subject completed the clinical study. If for any subject, study treatment or observations were discontinued, the reason(s) will be recorded.

The Investigator can discontinue a subject at any time if it is considered medically necessary.

In addition, subjects WILL be withdrawn from the study, in consultation with the Medical Monitor and the Investigator, if any of the following are met:

- A subject is significantly non-compliant with the requirements of the protocol.
- The investigator determines that it is in the best interest of the subject.
- Subject chooses to withdraw or is withdrawn due to an adverse event
- A subject becomes pregnant

Note: *The pregnancy will be followed to term for safety follow-up. Relevant safety information collected after the study has completed will be reported as supplemental information.*

- Discontinuation of study by Sponsor

Premature withdrawal from the study MAY occur if, in consultation with the Medical Monitor and the Investigator, any of the following are met:

- A subject is treated with a prohibited medication.
- Major protocol violation

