5.2.1 Discontinuation of Study Treatment

Discontinuation of study treatment and resumption of previous antiretroviral therapy is recommended if:

- Subject experiences virologic failure (defined as two consecutive HIV-1 RNA levels of ≥ 400 copies/ml separated by at least 3 days)
- Develops retroviral rebound syndrome or AIDS-defining conditions as specified in Appendix I ([Section 17.1](#)).
- Shows signs or symptoms of clinically significant immunosuppression
- Subject or the subject's clinician wishes to restart ART.
- Subject becomes pregnant.

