5.2.2 Data Collected for Withdrawn Subjects

Patients may withdraw from the study or discontinue study treatment at any time; however, CytoDyn, Inc. is dedicated to minimizing missing data in this study. It is therefore suggested that all patients, regardless of whether they continue to receive study treatment, continue within the study.

Investigators considering discontinuing study treatment should contact the medical monitor prior to such discontinuation. Patients who have study treatment discontinued will continue to be followed, per protocol, whenever possible. Patients who have study treatment discontinued due to a serious adverse event will be followed until resolution or stabilization of the event.

In the event that a subject is withdrawn from the study at any time due to an adverse event or serious adverse event (SAE), the procedures stated in [Section 9.1.1](#) or [9.3](#), respectively must be followed.

Every attempt should be made to collect follow-up information. The reason for withdrawal from the study will be recorded in the source documents and on the appropriate page of the eCRF.

Before a subject is identified as lost-to-follow up, the site should make all reasonable efforts to contact the subject. These attempts must be documented and should include at a minimum one phone call and one certified letter.

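### Section 5.2 orders study withdrawal for non-compliance and pregnancy while 5.2.2 asks all subjects to stay in, which permits outcome-linked loss of viral-load data

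*Protocol*

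**What the plan says.** Section 5.2 (Subject Withdrawal) states that "subjects WILL be withdrawn from the study, in consultation with the Medical Monitor and the Investigator, if any of the following are met". One entry in the list is "A subject is significantly non-compliant with the requirements of the protocol". The others are the investigator's view of the subject's best interest, pregnancy, the sponsor ending the study, and "Subject chooses to withdraw or is withdrawn due to an adverse event". A second list, of events that only may lead to withdrawal, holds prohibited medication and major protocol violation.

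Section 5.2.2, having given the reduction of missing data as its aim, continues: "It is therefore suggested that all patients, regardless of whether they continue to receive study treatment, continue within the study". It adds: "Patients who have study treatment discontinued will continue to be followed, per protocol, whenever possible".

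Section 5.2.1 begins "Discontinuation of study treatment and resumption of previous antiretroviral therapy is recommended if" and lists virologic failure, retroviral rebound syndrome or an AIDS-defining condition, signs of immunosuppression, a wish to restart antiretrovirals, and pregnancy. Non-compliance is not listed. Under Section 4.2, subjects who meet a 5.2.1 criterion other than virologic failure "will undergo TE161 Visit assessments and enter the Follow-up Phase of the study".

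The primary endpoint is time to virologic failure on monotherapy, meaning a viral load of 400 copies/mL or more that is confirmed at least 3 days later (Section 8.2.1). The primary analysis is per protocol (8.7.4.1) without imputation (8.6.4). An ITT analysis checks consistency (8.7.4.3).

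**The concern.** Stopping study treatment and leaving the study are different events with different consequences for the data. Section 5.2 merges them for some reasons, while 5.2.1, 5.2.2 and 4.2 keep them apart. A site with a non-compliant subject finds a mandatory instruction to withdraw in one section and a suggestion to retain in another.

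This matters statistically because the reasons in Section 5.2 are not neutral. Poor compliance, or a judgment that leaving is in the subject's interest, can plausibly go with a rising viral load. If such a subject leaves before a confirming sample, the failure is never recorded and the person is censored or left with an unknown outcome. Censoring linked to the outcome makes suppression look better than it is. The SAP can choose a censoring rule, but it cannot recover samples that were never drawn.

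**Working it through.** The protocol has no sample size, power or drop-out figure to reproduce (Section 8.3). The check is a comparison of passages, with arithmetic only to show scale.

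**1. The passages side by side**

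| Reason | Section 5.2 | Sections 5.2.1 and 4.2 | Exit viral load required? |
|---|---|---|---|
| Significant non-compliance | Study withdrawal, mandatory | Not listed | No |
| Best interest | Study withdrawal, mandatory | Not listed | No |
| Pregnancy | Study withdrawal, mandatory | Treatment stop, TE161 assessments, Follow-up Phase | By 4.2 yes; by 5.2 no |
| Major violation, prohibited medication | Study withdrawal, optional | Not listed | No |

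Pregnancy is a direct collision. Non-compliance conflicts with 5.2.2 only, but it has no binding exit sample. Section 5.2 is also uneven within itself: significant non-compliance is mandatory while a major violation is optional.

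**2. Where a failure can be lost**

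HIV-1 RNA is drawn every second week to TE58 and at least every four weeks beyond TE60 (Section 7.10.6). The between-visit repeat draw, for values above 200 copies/mL, is at the investigator's discretion (4.2). Without that repeat, a first raised value stays unconfirmed for about 2 weeks early on and up to about 4 weeks later. A withdrawal in that gap removes the event.

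**3. Bounds on the failure proportion**

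With m observed failures, k subjects of unknown outcome and n in total, the proportion lies between m/n and (m + k)/n, a width of k/n. The two values of n are the planned maximum of 28 (synopsis) and the 23 of 43 who completed the parent study without failure (Section 1.5.2.7).

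- k = 1: 1/28 = 3.6 points; 1/23 = 4.3 points.
- k = 5: 5/28 = 17.9 points; 5/23 = 21.7 points.

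**4. Direction of bias in the curve (assumed inputs)**

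Suppose a share q of subjects about to fail leave just before confirmation and are censored. With a constant hazard, Kaplan-Meier then estimates S^(1−q) where the true failure-free probability is S.

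| True S at 160 weeks | q = 10% | q = 20% | q = 30% |
|---|---|---|---|
| 0.50 | 0.5^0.9 = 0.54 | 0.5^0.8 = 0.57 | 0.5^0.7 = 0.62 |
| 0.70 | 0.7^0.9 = 0.73 | 0.7^0.8 = 0.75 | 0.7^0.7 = 0.78 |

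Simulation with n = 28 gave 0.536, 0.573 and 0.614 in the first row and 0.723, 0.752 and 0.782 in the second. The protocol supplies neither S nor q, so this shows direction and not a predicted size.

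**5. The comparison with 30 days (Section 8.7.4.1)**

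A sign-type test at an assumed one-sided 0.025 stands in for the comparison of the median with 30 days.

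- If time runs from the start of monotherapy in the parent study, every entrant has already passed 12 × 7 = 84 days. Then p = 0.5^28 = 3.7 × 10⁻⁹, or 0.5^23 = 1.2 × 10⁻⁷. Later withdrawals cannot change this.
- If time runs from TE1, only withdrawals in the first 30 days matter. The test needs 20 of 28 (p = 0.018) or 17 of 23 (p = 0.017) beyond 30 days, so it tolerates 8 or 6 subjects at or below that point.

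**The case against.** The strongest reply is that this is loose drafting with little effect. Several parts of it stand.

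- Section 5.2.2 concerns withdrawn subjects, so it presupposes that some leave; it only suggests retention. Section 5.2 requires consultation before withdrawal. It is not established that the mandatory wording prevails at sites.
- Subjects who stop treatment resume antiretrovirals, so failure on monotherapy is no longer observable even if they stay. This is right for 5.2.1 reasons. Non-compliance is not one of them: only Section 5.2 removes that subject from viral-load monitoring.
- The PP set excludes major violators whether or not they are withdrawn. That is so, but the ITT analysis meant to check the PP result needs the data that withdrawal removes.
- Non-compliance with protocol requirements need not mean missed doses, and nothing says removal comes before confirmation. The mechanism is therefore permitted, not demonstrated.

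A reader might also infer three stronger points that the protocol does not support. First, that Section 5.2 orders withdrawal for adverse events: its bullet describes a withdrawal already chosen or decided. Second, that withdrawal ends safety follow-up: Sections 5.2.2, 9.1.1 and 9.3.1 keep event follow-up in place, and 5.2 itself has pregnancies followed to term. Third, that the comparison with 30 days is endangered: step 5 of the working shows that it is hardly affected.

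**Conclusion.** The conflict is real and the passages must be reconciled. As written, the withdrawal rule permits viral-load data to be lost for reasons linked to the outcome. It does not by itself prove that this will happen. What is exposed is the time-to-failure curve, the secondary failure proportion and the supportive ITT analysis, which carry the stated objective of long-term efficacy.

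The size cannot be derived from the protocol, which gives no withdrawal rate or distribution of reasons. The only assumption-free statement is the k/n bound: in a study this small, each unknown outcome costs roughly 4 percentage points of certainty. Any figure for bias in the curve depends on an assumed share of failures lost. The point is worth correcting because the remedy is cheap; it does not undermine the primary test.

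**What to change.** In Section 5.2, separate discontinuation of study treatment from withdrawal from the study. Reserve the latter for withdrawn consent, loss to follow-up or the sponsor ending the study. List non-compliance and the other reasons as reasons for stopping treatment or as recorded deviations. Which events stop treatment remains the sponsor's clinical decision.

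Make the Section 4.2 exit assessments, including HIV-1 RNA, and the Table 4-9 follow-up visits apply to every early exit, and align 5.2.1 and 5.2.2 with this in binding language. Record whether the exit sample preceded the restart of antiretrovirals, because a later value cannot show failure on monotherapy.

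The cost is wording plus a few extra visits of a type already in the schedule. The change does not recover long-term outcomes once a subject is back on antiretrovirals. It does secure an exit viral load that can settle a pending raised value.
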